1.4. Breath Tests

Breath tests that are based on monitoring the ¹³CO₂, which is a by-product of ¹³C labeled substrates metabolism by the liver, have been proposed as a tool for non-invasive evaluation of liver health and have been used for over 30 years.

Methacetin may be utilized for the evaluation of liver functional capacity and/or the extent of liver impairment. The biochemical basis for the evaluation of functional capacity is that the compound is metabolized by the cytochrome P450 enzyme CYP1A2. Diseases of the liver that cause a loss in functional mass and/or impact the metabolic function of CYP1A2 in hepatic microsomes hepatocytes are associated with and may be correlated to a decrease in the liver capacity to metabolize Methacetin.

One of the most common methods for determining the rate of metabolism of Methacetin is to analyze the rate of metabolism of the methoxy group (CH₃O) of Methacetin to carbon dioxide, which is excreted in exhaled breath. To distinguish the carbon dioxide derived from Methacetin from all other sources of carbon dioxide, the methoxy group is labeled with ¹³C, a stable isotope of carbon. Thus all the CO₂ derived from Methacetin will contain ¹³C (¹³CO₂) in contrast to all other sources of CO₂, which will contain approximately 99% ¹²C, and 1% ¹³C, the naturally abundant isotope. Thus, the rate of excretion of CO₂ (normalized

| | |
|--|--|
| Exalenz Bioscience Ltd. | Last update on: April 01, 2015 |
| Protocol: The predictive value of the BreathID, ¹³ C-Methacetin breath test for Hepatic Decompensation; a retrospective analysis | Version Level: 1b |
| Document No.: CSD00074 | Page 9 of 23 |

to CO₂) above background following the administration of Methacetin-methoxy-¹³C indicates its rate of metabolism, which relates to the hepatic cell "health" and to the functional mass of the liver.

1.5. BreathID® System:

Exalenz has developed the BreathID device to perform automatic breath tests based on a unique molecular correlation spectrometer (MCS). Based on specific optical-radiation emission and absorption by ¹³CO₂ and ¹²CO₂ gases, the portable BreathID MCS device continuously senses exhaled breath and analyzes CO₂ in real-time through a nasal cannula worn by the patient. The primary output of the BreathID is the PDR (percentage dose recovery) and CPDR (Cumulative PDR) which quantify the amount of ¹³C labeled substrate metabolized by the liver..

1.6. ¹³C-labeled substrate - ¹³C-Methacetin:

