1.7.1. Hepatic Impairment Score Using the BreathID MBT

Exalenz has developed an algorithm for the scoring of hepatic impairment in patients suffering from a wide range of chronic liver diseases. The algorithm developed was named the "Hepatic Impairment Score" (HIS). The HIS is a probability score based on breath test and other demographic parameters. It was developed using logistic regression methodology. The linear predictor of the model selected is transformed into a probability score of disease severity. The HIS is intended to be used as the device output.

The use of the MBT test and its resultant continuous HIS for a particular patient enables the practitioner to assess the liver disease severity. This claim/label of the MBT is supported by several medical key opinion leaders (KOL).

Assessing the severity of chronic liver disease is important for following reasons:

- To make a timely decision to perform liver biopsy

| | |
|--|--|
| Exalenz Bioscience Ltd. | Last update on: April 01, 2015 |
| Protocol: The predictive value of the BreathID, ¹³ C-Methacetin breath test for Hepatic Decompensation; a retrospective analysis | Version Level: 1b |
| Document No.: CSD00074 | Page 10 of 23 |

- To aid in assessment of the risk of developing cirrhosis and its complications, including bleeding varices, infections, ascites, and hepatic encephalopathy.
- To decide when to initiate certain diagnostic investigations and therapeutic interventions including: Anti -viral treatment, upper endoscopy, use of beta blockers for varices and determination of frequency of monitoring of disease progression.
- To decide when to begin surveillance for liver cancer, such as blood tests (serum levels of alpha feto protein) and imaging (ultrasound).
- To decide when to prepare or list a patient for liver transplantation.

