3. ENDPOINTS

3.1. Primary Efficacy Endpoints

The MBT results and the time to hepatic decompensation events:

Hepatic decompensation is defined as the occurrence of at least one of the following events in the time frame between the last ¹³C-Methacetin Breath Test (MBT) to the time of data collection:

1. Death (liver related)
2. Transplantation (cadaveric and living donors)
3. Ascites
4. HE (Hepatic Encephalopathy)
5. Newly diagnosed varices or variceal bleeding
6. SBP (spontaneous bacterial peritonitis)/Sepsis
7. HRS (Hepatorenal syndrome)
8. HCC (hepatocellular carcinoma)
9. Increase in CTP (Child Turcotte Pugh) Score by 3 points
10. Increase in MELD score by 5 points

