8.6. Statistical Analyses

All statistical analyses and data presentations, including tabulations and listings, will be performed using the SAS version 9.3 (or higher) software. Statistical tests will be two-sided and the level of significance is 0.05. Nominal p-values will be presented.

Baseline demographics and medical characteristics will be presented in tabular format. The statistical evaluation of baseline characteristics will include all available data.

For continuous variables, the following descriptive statistics will be given: N, Mean, Standard Deviation, Minimum, Median and Maximum values; for discrete variables, the Frequency and Percentage of patients or events will be provided.

For comparison of means (continuous variables), the two-sample t-test or the Wilcoxon rank sum test will be used as appropriate. For comparison of proportions (categorical variables), the Chi-squared test or Fisher's exact test will be used as appropriate.

Kaplan-Meier curves of the time event data will be presented. For comparison of time to event data, the log rank test will be used. Cox regression will be used to estimate hazard ratios, their level of significance and 95% confidence limits.

Risk stratification may be performed by categorizing the MBT into risk groups, for these groups Kaplan-Meier Curves of the time to clinical outcome will be presented for the MBT categories as well as the liver biopsy results to compare predictive value.

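### The analysis section does not say which breath-test measure is the predictor, and its only MBT-versus-biopsy comparison uses optional risk groups with no cut-points

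*Combined protocol and SAP*

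**What the plan says.** All references are to the combined protocol and SAP.

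- **Predictor.** Sections 3.1 and 8.2 give the primary endpoint as "The MBT results and the time to hepatic decompensation events". They fix which test counts when a patient had several (the last one), but not which quantity is read from it. The data list in section 6.2.1 also says only that MBT results are recorded.
- **Candidate measures.** Section 1.5 states: "The primary output of the BreathID is the PDR (percentage dose recovery) and CPDR (Cumulative PDR". Section 1.7.1 describes HIS, a continuous probability score built from the breath test and demographic parameters, and adds: "The HIS is intended to be used as the device output".
- **Tests.** Section 8.6: "For comparison of time to event data, the log rank test will be used". It also lists Cox regression for hazard ratios, without naming a covariate or its scale. The error rule is: "Statistical tests will be two-sided and the level of significance is 0.05. Nominal p-values will be presented".
- **Risk groups and biopsy.** Section 8.6: "Risk stratification may be performed by categorizing the MBT into risk groups". Kaplan-Meier curves "will be presented for the MBT categories as well as the liver biopsy results to compare predictive value". It states no number of groups, no cut-points and no rule for choosing them.
- **Aims.** Section 1.10 says the data will validate a prognostic hypothesis. Sections 2 and 8.1 aim to show that the MBT predicts outcome better than biopsy; section 8.1 adds MELD as a comparator.

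**The concern.** A study meant to validate a prognostic test needs its predictor fixed before the outcomes are joined to it. Here the breath tests date from 2008-2012 and the outcomes already sit in patient files, so both halves of the data exist. Nothing in the plan requires the measure or the grouping to be chosen before the two are linked, and no multiplicity adjustment accompanies the nominal p-values. An analyst could follow the plan to the letter and still choose the measure and cut that separate the curves best.

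The biopsy comparison has a second weakness. Two sets of Kaplan-Meier curves give no estimate of the difference in predictive ability, no confidence interval and no test. Section 5 admits patients with or without a valid biopsy, so the two sets of curves need not describe the same patients. Section 1.10 suggests that many patients could avoid biopsy if the MBT predicts better, and this comparison is the only stated support for that.

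**Working it through.** **The plan's own figure.** Section 8.5 gives 414 + 165 = 579, which reproduces. It is a ceiling from earlier enrolments. There is no power, event or effect-size calculation to check.

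**Do sections 1.5 and 1.7.1 conflict?** Section 1.5 describes what the instrument measures (PDR, CPDR). Section 1.7.1 describes a score computed from that measurement plus demographic parameters. One is raw and the other derived, so both statements can be true. The gap is that section 8.6 does not choose between them.

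**How much can free choice matter?** The MBT was simulated as unrelated to outcome.

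Inputs from the documents:
- Two-sided 0.05, nominal (section 8.6), so the critical value is 1.96.
- N up to 579 (section 8.5).
- 3-5% events per year (synopsis, stated for stable cirrhosis).
- Tests from August 2008 to September 2012 and a protocol dated April 2015. Follow-up therefore runs from about 2.6 years (2 years 7 months) to 6.7 years (6 years 8 months).

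Assumptions:
- N of 300 as a lower case.
- The 3-5% rate applied to all patients.
- Uniform censoring from 2.5 to 6.7 years.
- Three candidate measures, each pair correlated 0.8.
- The sets of cuts listed below.
- Only the most favourable result is reported.

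Formulas. For patient i with event indicator d and follow-up y, the residual is m = d - H(y), where H is the Nelson-Aalen estimate and s² is the variance of m.
- Cut after the k lowest MBT values: Z(k) = |sum of those k residuals| / sqrt(s² k(n-k)/n).
- Continuous term: Z = |Σ(x - x̄)m| / sqrt(s² Σ(x - x̄)²).
- Reject when the largest Z among the permitted choices exceeds 1.96.

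| Choice permitted | Type I error |
|---|---|
| One pre-set continuous measure | about 5% |
| One measure, pre-set median cut | about 5% |
| Best of three continuous measures | about 10% |
| Best of five conventional cuts (quartiles, tertiles, median) | 15-16% |
| Best of 17 cuts, 10th-90th percentile | 29-31% |
| Best of three measures and 17 cuts | 54-57% |

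With 2,000 data sets, the standard error near 30% is sqrt(0.3 × 0.7 / 2000) = 0.010, or about one percentage point.

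**Sensitivity** (N = 579, censoring at 2.5-6.5 years):
- Event rates of 2%, 5% and 7% per year (about 50, 116 and 155 events) hardly change the results.
- Searching every cut from the 10th to the 90th percentile gives 45-46%.
- Three measures at a fixed median cut give 10-13% for assumed correlations of 0.9 to 0.5. The value for independent measures is 1 - 0.95³ = 0.143.

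**The case against.** The strongest reply is that the plan already allows a sound analysis. Section 1.7.1 calls HIS continuous, and section 8.6 lists Cox regression separately from risk stratification. A single continuous HIS term would satisfy the text and need no cut-point. The risk-group sentence is optional, promises curves rather than a primary p-value, and nowhere says cuts will be optimised.

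Much of that stands, and it rules out several stronger readings:

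- A reader might infer that sections 1.5 and 1.7.1 contradict each other. They do not.
- A reader might infer that the primary p-value will come from a chosen cut. The plan does not tie a primary test to the groups. The log-rank sentence is general, so this is possible but not stated.
- A reader might infer that the hazard ratio will be overstated and fail to replicate. That would need optimised cuts, and no hazard-ratio bias was computed. Section 1.10 reports earlier hazard ratios of up to 12, so the no-association case is not the only relevant one.
- A reader might attach a fixed information loss to grouping. The familiar 2/π (64%) retained assumes a normal predictor split at its median. HIS is a probability score and no median split is planned.

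What the reply does not remove is that a continuous analysis is permitted but not specified. The measure would remain open even then, and that alone takes the error from about 5% to about 10% under the stated assumptions. Nor is the grouping labelled exploratory, although it is the only stated comparison with biopsy.

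**Conclusion.** The point holds as an unspecified predictor and an inadequate comparison method. Sections 3.1, 8.2 and 8.6 do not fix the measure, its time point or its scale. The one stated MBT-versus-biopsy comparison cannot show superiority and leaves the groups open to choice after outcomes are seen.

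The size is illustrative: about 10% to 57% type I error against a nominal 5%, depending on how much choice is exercised. The range depends on the assumed number of measures, their correlation, the cuts searched and reporting only the best result. It hardly depends on sample size or event rate. It concerns the MBT against no association; the error in the claim that the MBT beats biopsy was not simulated. The documents show that such choices are open, not that they are intended.

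This should be corrected before outcomes are linked to breath-test results.

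**What to change.** In sections 3.1 and 8.6 (and 8.2, to match):

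1. Name one MBT measure, with its time point where relevant, as the sole primary predictor, and test it as a continuous term in the Cox model.
2. Compare it with biopsy stage by the difference in C-index with a 95% confidence interval, in patients who have both.
3. If HIS is chosen, state that it includes demographic parameters, and also report a breath-only measure. Otherwise the comparison is not breath test against biopsy.
4. Use risk groups for Kaplan-Meier display only. Base them on MBT quantiles, or on earlier cut-points if any exist (the documents give none), fixed before outcomes are linked.
5. Label all other measures and cuts exploratory.

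The cost is a few sentences, a little more analysis work and the loss of freedom to choose the grouping. No new data are needed.

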| Document No.: CSD00074 | Page 3 of 23 |

| | | |
|---------|--|----|
| 8. | STATISTICAL CONSIDERATIONS..... | 15 |
| 8.1. | STUDY DESIGN AND OBJECTIVES..... | 15 |
| 8.2. | PRIMARY ENDPOINT | 15 |
| 8.3. | SECONDARY ENDPOINT | 15 |
| 8.4. | SAFETY ENDPOINTS | 15 |
| 8.5. | SAMPLE SIZE..... | 15 |
| 8.6. | STATISTICAL ANALYSES..... | 16 |
| 9. | ADVERSE EVENTS..... | 16 |
| 10. | STUDY ADMINISTRATION..... | 16 |
| 10.1. | REGULATORY AND ETHICAL CONSIDERATIONS | 16 |
| 10.1.1. | Informed Consent | 16 |
| 10.1.2. | Institutional Review Board | 16 |
| 10.1.3. | End of the study | 17 |
| 10.2. | INVESTIGATOR RESPONSIBILITIES | 17 |
| 10.3. | DATA MANAGEMENT | 17 |
| 10.4. | STUDY MONITORING | 17 |
| 10.5. | SUBJECT CONFIDENTIALITY | 17 |
| 10.6. | QUALITY ASSURANCE..... | 18 |
| 10.7. | RETENTION OF ESSENTIAL STUDY DOCUMENTS | 18 |
| 10.8. | AGREEMENTS..... | 18 |
| 11. | PUBLICATION | 18 |
| 12. | REFERENCES..... | 18 |

| | |
|--|--|
| Exalenz Bioscience Ltd. | Last update on: April 01, 2015 |
| Protocol: The predictive value of the BreathID, ¹³ C-Methacetin breath test for Hepatic Decompensation; a retrospective analysis | Version Level: 1b |
| Document No.: CSD00074 | Page 4 of 23 |

SYNOPSIS

Investigational Product:

0.05% ¹³C-Methacetin solution and the BreathID® Device

Phase of Development:

Retrospective clinical investigation

Background:

This study is a follow up study to be conducted in selected sites, that participated in Exalenz' Pivotal HIS-EX-408 and/or PLT-BID-1108 study using the MBT in chronic liver patients. The aim of the study was to compare the breath test to the liver biopsy to assess the capability to detect cirrhosis.

Study Rationale:

Previous studies have shown that the MBT can be used to predict liver decompensation. In the present study Exalenz wishes to evaluate the prognostic value of MBT and Biopsy in a long term retrospective surveillance of the described study population.

Objectives:

To evaluate the ability of the MBT to predict hepatic decompensation events, in patients with chronic liver disease.

Primary outcome measures: MBT results and Hepatic decompensation measured with the time to each event, defined as the occurrence of at least one of the following events in the time frame between the last ¹³C-Methacetin Breath Test (MBT) to the time of data collection:

1. Death (liver related)
2. Transplantation (cadaveric and living donors)
3. Ascites
4. HE (Hepatic Encephalopathy)

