It is anticipated that 3-5% of patients with stable cirrhosis will develop hepatic decompensation and achieve an end-point within a year. An additional 1-2% would be expected to die from these complications per year. This study is conducted 6 years post initial enrollment, accordingly the expected amount of complications are expected to be 6 times higher. Furthermore some of the patients that were not considered as cirrhotic at the time of enrollment may progress to cirrhosis and deteriorate.

| | |
|--|--|
| Exalenz Bioscience Ltd. | Last update on: April 01, 2015 |
| Protocol: The predictive value of the BreathID, ¹³ C-Methacetin breath test for Hepatic Decompensation; a retrospective analysis | Version Level: 1b |
| Document No.: CSD00074 | Page 6 of 23 |

All patients with valid breath test results from the HIS-EX-408 and/or PLT-BID-1108 trials will be candidates for this follow up trial.

Analyses:

All statistical analyses and data presentations, including tabulations and listings, will be performed using the SAS version 9.3 (or higher) software. Statistical tests will be two-sided and the level of significance is 0.05. Nominal p-values will be presented.

The ability of MBT to predict morbidity and mortality and other complications will be evaluated using survival analysis methods, mainly Kaplan-Meier curves and Cox regression analyses.

| | |
|--|--|
| Exalenz Bioscience Ltd. | Last update on: April 01, 2015 |
| Protocol: The predictive value of the BreathID, ¹³ C-Methacetin breath test for Hepatic Decompensation; a retrospective analysis | Version Level: 1b |
| Document No.: CSD00074 | Page 7 of 23 |

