2. OBJECTIVES

The objectives of this study are:

- To evaluate the ability of the Methacetin Breath Test to detect hepatic decompensation events
- To evaluate the relationship between liver Biopsy and clinical outcome and show that the MBT has a better predictive ability of clinical outcome than liver biopsy.

| | |
|--|--|
| Exalenz Bioscience Ltd. | Last update on: April 01, 2015 |
| Protocol: The predictive value of the BreathID, ¹³ C-Methacetin breath test for Hepatic Decompensation; a retrospective analysis | Version Level: 1b |
| Document No.: CSD00074 | Page 12 of 23 |

- To evaluate the ability of the MBT to predict each of the individual liver related complications.

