8. STATISTICAL CONSIDERATIONS

8.1. Study Design and Objectives

This is a retrospective, multi-center, non-randomized, open label study of the ¹³C-Methacetin BreathID Test (MBT) that will include all patients previously enrolled into the BreathID pivotal study who have performed a valid MBT.

The main objective of the study is to evaluate the ability of the MBT to predict time to hepatic decompensation events.

The secondary objective of the study is show that MBT predictive ability is better than that of liver biopsy/MELD in predicting time to these events.

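### The stated aim is to show that MBT predicts better than liver biopsy and MELD, but section 8.6 plans no estimate of the difference between markers

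*Combined protocol and SAP*

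**What the plan says.** **Objectives.** Section 2 includes the aim to "show that the MBT has a better predictive ability of clinical outcome than liver biopsy". The secondary objective in section 8.1 is to "show that MBT predictive ability is better than that of liver biopsy/MELD in predicting time to these events". The synopsis objective makes no comparative claim: "To evaluate the ability of the MBT to predict hepatic decompensation events, in patients with chronic liver disease". Section 1.10 adds that, if MBT turns out to predict better than biopsy, many patients could avoid a biopsy.

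**Analysis.** The synopsis says that the predictive ability of MBT "will be evaluated using survival analysis methods, mainly Kaplan-Meier curves and Cox regression analyses". Section 8.6 adds the log-rank test, Cox hazard ratios with 95% limits, a two-sided 0.05 level and nominal p-values, all in general terms. On comparing markers it says only this: "Risk stratification may be performed by categorizing the MBT into risk groups", and for those groups Kaplan-Meier curves "will be presented for the MBT categories as well as the liver biopsy results to compare predictive value". No cut-offs are given, and MELD is not mentioned in 8.6.

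**Endpoint and population.** The secondary endpoint in section 8.3 relates biopsy to clinical outcome and does not compare it with MBT. Section 5 admits patients whether or not they have a valid biopsy. No common set of patients is defined for a comparison.

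**The concern.** A claim that one marker predicts better than another concerns a difference, so it needs an estimate of that difference and its uncertainty. The planned tools do not give one:

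- A log-rank test compares groups of patients. MBT and biopsy are two measurements on the same patients.
- Separate hazard ratios for markers on different scales, or with different categories, cannot be compared directly.
- One marker reaching p < 0.05 while another does not is not a test of the difference between them.
- The Kaplan-Meier display may not be produced at all. If it is, the MBT cut-offs could be chosen after outcomes are known.
- For MELD, no comparison of any kind is stated.

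At stake is the comparative conclusion, which section 1.10 links to avoiding biopsy.

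**Working it through.** **1. The plan's own size figure.** 414 + 165 = 579, as stated in section 8.5. This is the number of patients available, not a powered size. No event target, effect size or power is given for the comparison.

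**2. Plausible event counts.** The synopsis gives two rates: "It is anticipated that 3-5% of patients with stable cirrhosis will develop hepatic decompensation and achieve an end-point within a year" and "An additional 1-2% would be expected to die from these complications per year". It multiplies by 6 for six years. I take 3% per year as the low rate and 5% + 2% = 7% as the high rate. Adding deaths gives an upper bound, because a death from a complication follows an event already counted. The share of cirrhotic patients is not stated; 25-50% is my assumption.

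- Six years for everyone: 579 × 0.25 × 6 × 0.03 = 26, and 579 × 0.50 × 6 × 0.07 = 122.
- Compounded: 579 × 0.25 × (1 − 0.97^6) = 24, and 579 × 0.50 × (1 − 0.93^6) = 102.
- Follow-up implied by the dates: testing from August 2008 to September 2012 and a protocol date of April 2015 give 2.58 to 6.67 years. If testing was spread evenly, the mean is (2.58 + 6.67)/2 ≈ 4.6 years.
- At that mean: 579 × 0.25 × 4.625 × 0.03 = 20, and 579 × 0.50 × 4.625 × 0.07 = 94 (19-83 compounded).

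None of these counts includes progression in patients who were not cirrhotic at testing.

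**3. What separate tests do when neither marker is better.** Simulation: two equally good, normally distributed markers with correlation 0.5; exponential survival with log hazard linear in both; N = 579; uniform follow-up of 2.58-6.67 years; a separate log-rank test on each marker split at its median. Ranges are across repeat runs. The table shows how often one marker is significant and the other is not, in either direction.

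| C-index of each marker | about 31 events | about 65 events | about 120 events |
|---|---|---|---|
| 0.70 | 17-18% | 1% | 0% |
| 0.61 | 37% | 32-35% | 11-14% |

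The markers are equally good, so about half of each figure favours MBT. Runs that counted this direction separately, at slightly lower event numbers, gave about 10%, 1% and 0% at 0.70, and 18%, 15% and 7% at 0.61.

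**4. How precise a direct comparison would be.** With C about 0.70, the standard deviation of the paired difference in Harrell's C was 0.051, 0.035 and 0.026 at 31, 65 and 121 events. The 95% half-widths are therefore:

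- 1.96 × 0.051 = 0.10
- 1.96 × 0.035 = 0.07
- 1.96 × 0.026 = 0.05

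As a rule of thumb, the half-width is 0.54-0.59 divided by the square root of the number of events. At 20 events this gives 0.12-0.13, and at 94 events about 0.06.

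**5. Power of a lower-limit-above-zero rule.**

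- True C difference of about 0.05: 17-18% at 32 events, 29-30% at 66, 47-50% at 122.
- True C difference of about 0.10: 50-52% at 34 events, 79-84% at 69, 96-98% at 125.

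Two equally good continuous markers meet the rule in 2-4% of studies.

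**The case against.** The strongest reply is that this is a secondary objective in a retrospective study that reports nominal p-values. The synopsis objective is not comparative, the biopsy endpoint in 8.3 is not either, and section 1.10 states a conditional benefit rather than a decision rule. The synopsis word for its methods leaves room for others, so a Cox model with both markers is not excluded. All of this stands, and it limits the impact. It does not remove the gap: sections 2 and 8.1 still set out to show superiority, and no joint model or measure of difference is specified.

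Three stronger readings are tempting but not supported:

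- **That the simulated percentages are the plan's error rate.** They rest on assumed markers, correlation and event counts, and the plan does not say that separate p-values would decide the matter. Chance gaps in the C-index would be further still from an error rate of the plan, because the plan never computes one.
- **That about 120 events should be expected.** That figure needs the highest rates and six years for everyone. On the 4.6-year mean follow-up the upper figure is 94, unless progression in non-cirrhotic patients adds to it.
- **That the study's main result is in doubt.** The Cox and Kaplan-Meier analyses suit the question of whether MBT predicts events.

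**Conclusion.** The point holds for the comparative objective only. The stated analysis cannot support a conclusion that MBT predicts better than biopsy, and for MELD no comparison is stated. This follows from the text and does not depend on the simulation.

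The size does depend on assumptions. Contradictory significance between two equally good markers is common with about 31 events (17-18% at C 0.70, 37% at C 0.61), rare at C 0.70 from about 65 events on, and still 11-14% at C 0.61 with 120 events. About half of it favours MBT. A direct comparison would carry a 95% half-width of about 0.10, 0.07 and 0.05 at those event counts. It would be wider if the set with both markers is smaller than 579, and the documents do not say how much smaller. The matter should be fixed before outcome data are analysed. The primary objective and the descriptive biopsy endpoint stand as they are.

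**What to change.** **Option 1 (preferred).** Reword the comparative objective in sections 2 and 8.1 as descriptive, in line with the synopsis objective. This costs wording only, and the low power for small differences favours it.

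**Option 2, if a superiority claim is kept.** Add to section 8.6:

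- one MBT measure, named before outcome data are seen;
- a paired difference in C-index, or an equivalent paired measure of discrimination, for time to first event, with a bootstrap 95% confidence interval;
- separate comparisons with biopsy and with MELD, each in patients who have both markers;
- for biopsy, the full stage rather than cirrhosis yes/no, with the handling of ties stated, because a coarse comparator loses discrimination merely from its scale;
- a claim of superiority over a comparator only if the lower limit is above 0.

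Keep the Kaplan-Meier curves as illustration.

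Optional additions are sensitivity analyses without the MELD-increase and CTP-increase components of the outcome, a likelihood-ratio test for the added value of MBT (not for superiority), and a smallest difference that would matter.

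Option 2 costs SAP text and a modest analysis, with low power as shown. For MELD it is feasible only if MELD at the time of the MBT can be retrieved. The data list in section 6.2.1 does not name it, although the MELD-increase component needs it.
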